#### 1.If SBP<100 mmHg:

- Increase dry weight by 0.2-0.5 kg until patient euvolemic
- If SBP still <100 mmHg, will titrate down/off patient's existing medications in the following order: anti-adrenergic; vasodilators; alpha blockers; calcium channel blockers;  $\beta$ -blockers; RAAS inhibitors

#### 2.If SBP 100-140 mmHg:

- No adjustment of dry weight or medications; recheck in two weeks

#### 3.If SBP>140 mmHg

- Decrease dry weight by 0.2-0.5 kg until patient euvolemic
- If SBP still >140 mmHg, will increase doses of patient's existing medications in the following order: RAAS inhibitors;  $\beta$ -blockers; calcium channel blockers; alpha blockers; vasodilators; anti-adrenergic
- If patient is at maximum tolerated doses of current medications and SBP>140 mmHg, will add doses (and titrate up) of new medication

classes in the following order (not duplicating classes with patient's existing medications): RAAS inhibitors;  $\beta$ -blockers; calcium channel blockers; alpha blockers; vasodilators; anti-adrenergic. Choice of specific anti-hypertension medications within each class will prioritize those that have low dialyzability and are covered by the patient's existing insurance coverage. The dialyzability characteristics of specific medications is outlined in the table below (from Georgianos and Agarwal CJASN 2016).

Drug Class and Drug	Usual Dosage	Route of Excretion	Removal with Dialysis, %	Supplement Dose for Dialysis, mg
Angiotensin-converting enzyme inhibitors				
Benazepril	5–40 mg every day	K (L)	20–50	5–10
Captopril	12.5–50 mg three times per day	K	50	12.5–25
Enalapril	2.5–10 mg every 12 h	K (L)	50	2.5–5
Fosinopril	10 mg every day	K (L)	None	None
Lisinopril	2.5–10 mg every day a	K	50	2.5–5
Perindopril	2–8 mg every day	K (L)	50	2
Ramipril	5–10 mg every day	K (L)	20	2.5
Trandolapril	0.5–4 mg every day	K (L)	30	0.5
Angiotensin receptor blockers				
Candesartan	8–32 mg/d	K (L)	None	None
Eprosartan	600–1200 mg/d	L	None	None
Irbesartan	75–300 mg/d	L	None	None
Losartan	50–100 mg every day	K (L)	None	None
Olmesartan	10–40 mg/d	K (L)	None	None
Telmisartan	40–80 mg/d	L	None	None
Valsartan	80–320 mg every day	K (L)	None	None
Mineralocorticoid receptor antagonists				
Spironolactone	25–50 mg every day	K (L)	None	None
Eplerenone	50–100 mg every day	K (L)	None	None
β-Blockers				
Atenolol	25 mg every day b	K (L)	50	25–50
Bisoprostol	2.5–20 mg every day	L	None	None
Carvedilol	25 mg twice a day	L (K)	None	None
Labetalol	200–600 mg twice a day	K (L)	None	None
Metoprolol	50–100 mg twice a day	K (L)	None	None
Nadolol	80–100 mg twice a day	K	50	80
Propranolol	80–160 mg twice a day	K	None	None
Calcium-channel blockers				
Amlodipine	2.5–10 mg every day	L	None	None
Felodipine	5–10 mg every day	L	None	None
Nicardipine	20–40 mg three times a day	L	None	None
Nifedipine XL	30–90 mg every day	L	None	None
Lacidipine	2–6 mg/d	L (K)	None	None
Manidipine	10–20 mg/d	L	None	None
Diltiazem CD	180–360 mg	L (K)	None	None
Verapamil CD	180–360 mg every day	L (K)	None	None
α-Adrenergic blockers				
Doxazosin	1–16 mg every day	L	None	None
Prazosin	1–15 mg twice a day	L	None	None
Terazosin	1–20 mg every day	L	None	None
Others				
Clonidine	0.1–0.3 mg twice a day/three times a day	K (L)	5	None
Hydralazine	25–50 mg three times a day/twice a day	L	25–40	None

K, kidney; L, liver.  
aPreferred dosage for lisinopril is 10–40 mg three times weekly after dialysis. The maximum dose recommended in hemodialysis patients is 40 mg per day.  
bPreferred dosage for atenolol is 25 mg–100 mg three times weekly after dialysis to maximize the antihypertensive effect and convenience of dosing.

A Schedule of Events representing the required testing procedures to be performed for the duration of the study is diagrammed in Appendix 1.

## 8.2 Clinical Assessments

### 8.2.1 Demographics

Demographic information (date of birth, gender, race/ethnicity) will be recorded at the Screening visit.

### 8.2.2 Medical History and Concomitant Medications

Relevant medical history, including history of current disease and concomitant medication use (including dose, route and frequency of administration) will be recorded at screening visit and updated at all follow-up study visits.

### 8.2.3 Blood pressure: Assessment of episodes and symptoms of intra-dialytic hypotension

We will review the dialysis record approximately every 2 weeks for all study participants to determine frequency of intra-dialytic hypotension (IDH; defined as intra-dialytic SBP<90 mmHg). This will be obtained from the dialysis unit medical record and quantified as % of sessions with IDH over the 4-month study duration. For symptoms assessment, we will contact participants (in both arms) once approximately every 2 weeks. Patients will be queried via interview (either phone or during dialysis) about adverse events noted during the past HD session(s) which will include symptoms of hypotension such as cramping (yes/no), dizziness/lightheadedness (yes/no) and fatigue (yes/no). We will also ask patients “how long did it take you to recover from your last dialysis treatment,” a validated question that is an important patient-centered outcome. Patient responses to this question will be reported in minutes.

### 8.2.4 Adverse Events

Information regarding occurrence of adverse events will be captured throughout the study. Outcomes in relation to study intervention will be recorded on the case report form (CRF).

## 8.3 Clinical Laboratory Measurements

Standard clinical laboratory measures will be documented for the study at all study visits. The University of Washington site will be collecting 10 ml of plasma and 10 ml of serum for planned biomarker measurements at the completion of the study. The University of Washington site will also collect 5 ml of serum for pregnancy test for women of childbearing potential at the screening visit.

## 9 EVALUATIONS BY VISIT

### 9.1 Visit 0: Screening visit

1. Review the study with the subject and obtain written informed consent and HIPAA authorization
2. Assign the subject a unique screening number.
3. Record demographics data.

4. Record medical history, including a history of ESRD, dialysis access, dialysis initiation date and history of prior kidney transplants through participant questionnaires and review of the medical record
5. Record concomitant medications through participant questionnaires and review of the medical record
6. Record and review previous pre-dialysis blood pressures from the prior 2 weeks
7. Record previous clinical laboratory values (with corresponding date) taken from the dialysis and other medical records
8. Administer questionnaire of symptoms of hypotension during the last hemodialysis session(s): cramping (yes/no), dizziness/lightheadedness (yes/no), and fatigue (yes/no).
9. Ask open-ended question: "How long did it take you to recover from your last dialysis session" (responses in minutes or hours)
10. Obtain blood (5 ml) for serum pregnancy test for women of childbearing potential.

## **9.2 Visit 1: Baseline Visit**

1. Update information obtained at screening visit
2. Record the following information from the dialysis records from the prior two weeks: estimated dry weight, pre-dialysis blood pressures, episodes of intra-dialytic hypotension
3. Randomize participant to one of two study arms
4. If participant is randomized to home BP arm, train participant on use and transmission of home BP measures
5. Schedule subject for next study contact in approximately 14 days, either during patient's regularly scheduled dialysis or a telephone call
6. Optional: Place 44-hour ambulatory blood pressure cuff and train patient on use (study team will also coordinate with patient return of 44-hour ambulatory blood pressure monitor.) Administer 44-Hour ABPM Experience Questionnaire.
7. Blood sample collected at beginning of dialysis treatment via dialysis access and usual dialysis procedures (at UW only)

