## 5.2 Secondary Outcomes

- Acceptability of a Bluetooth-enabled home BP monitor: of the home BP participants, we will determine the modality they choose to transmit their home BP readings (e.g. via Bluetooth, manual log, phone, etc)
- Differences in blood pressures between treatment groups as assessed by: (1) pre-dialysis SBP and DBP; (2) post-dialysis SBP and DBP and (3) 44-hour intra-dialytic ambulatory blood pressure monitoring from beginning to the end of the study (optional)

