### 7.3 Measuring Home SBP

We will use the Microlife WatchBP Home A BT device.

After appropriate training by study personnel, study participants will be asked to take their own BP at home every two weeks.

- Home BP will be taken on a non-dialysis day
- Participants will be instructed to obtain a BP measure in the morning on a non-dialysis day (3 consecutive BP measures obtained at one sitting)
- Participants will be instructed to obtain a BP measure in the evening on a non-dialysis day (3 consecutive BP measures obtained at one sitting)

Participants will have several options to share the home blood pressure readings with the study team.

- For participants with a smart phone, the BP readings can be automatically downloaded via Bluetooth to an app then to a secure cloud server.
- Participants can download the readings from the home blood pressure device via USB drive and shared with the study team.
- Participants can keep a paper log of home blood pressure readings to share with the study team.
- Participants can text, phone or email the results to the study team.

We will allow assistance from family members or other caregivers and work in other ways with study participants to minimize burden of data transmission.

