## 8 STUDY PROCEDURES AND GUIDELINES:

### 8.1 Approach to blood pressure management

For participants in the usual care treatment group, blood pressure readings measured for clinical purposes at the dialysis unit will be tracked, recorded and in response we will modify the dry weight and anti-hypertensive medications per algorithm below (including the date in which any adjustments to dry weight and medication dose were implemented).

For participants in the home blood pressure treatment group, we will track and record the home blood pressure measures and modify the dry weight and anti-hypertensive medications per algorithm below.

The following approach will be used to achieve SBP <140 mmHg and >100 in both treatment groups, which will be implemented every 2 weeks.

- Dry weight adjustment (with counseling on dietary sodium and fluid intake if appropriate)
- Adjustment of standard anti-hypertensive medications (e.g. angiotensin converting enzyme [ACE] inhibitors/angiotensin receptor blockers [ARB][collectively referred to as RAAS inhibitors];  $\beta$ -blockers; calcium channel blockers). The protocol will be as follows

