#### **9.4 Visit 9 (final study visit)**

1. Same procedures listed in for visits 2-8
2. Blood sample collected at beginning of dialysis treatment via dialysis access and usual dialysis procedures (at UW only)
3. Administer Home BP Device Experience Questionnaire.
4. Optional: Place 44-hour ambulatory blood pressure cuff and train patient on use (study team will also coordinate with patient return of 44-hour ambulatory blood pressure monitor). Administer 44-Hour ABPM Experience Questionnaire.

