## APPENDIX 1.

	VISIT 0 SCREENING VISIT	VISIT 1 Baseline Visit	VISITS 2-8 (in person during regularly scheduled dialysis or phone call) 14 (+/-7) days apart	VISIT 9
Informed Consent	X			
Medical History	X	X	X	X
Recording of vital signs, including blood pressure and weight	X	X	X	X
Review of medical and dialysis records	X	X	X	X
Medication review	X	X	X	X
Record laboratory values	X	X	X	X
Questionnaires on episodes and symptoms of high or low blood pressure	X	X	X	X
Randomization		X		
Teaching of home BP monitor		X		
Reviewing BP medications and pre- and post-dialysis weights			X	X
Review home BP readings (if applicable)			X	X
Concomitant Medication Review			X	X
Adjust EDW or BP medications			X	X
Adverse Experiences			X	X
44-hour ambulatory blood pressure monitor		X		X
Blood draw		X		X

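### Agreement to the optional 44-hour ABPM is not required before randomisation, and the final recording is not ordered against treatment adjustment at Visit 9

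*Combined protocol and SAP*

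**What the plan says.** Section 5.2 lists three between-arm blood pressure comparisons: pre-dialysis pressure, post-dialysis pressure ("2) post-dialysis SBP and DBP") and "44-hour intra-dialytic ambulatory blood pressure monitoring from beginning to the end of the study (optional". Section 7.2 states that neither investigators nor participants are blinded.

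The Visit 1 list in section 9.2 runs: item 3, "Randomize participant to one of two study arms"; item 4, home-BP training for those allocated to the home arm; item 6, "Optional: Place 44-hour ambulatory blood pressure cuff and train patient on use". Neither the Visit 0 list (section 9.1) nor the Visit 0 column of Appendix 1 contains an ABPM step.

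For the final visit, section 9.4 opens with "Same procedures listed in for visits 2-8". Item 12 of those procedures (section 9.3) is the adjustment of dry weight and medications. Item 4 of section 9.4 is the final ABPM, again optional. The Appendix 1 row "Adjust EDW or BP medications" is marked for Visits 2-8 and Visit 9, and the ABPM row for Visits 1 and 9.

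Section 14.1 includes all randomised patients, and no rule covers those without ABPM. Section 14.4 plans descriptive statistics for changes in pre-dialysis pressure and for ABPM at the end of the study.

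**The concern.** Each arm is titrated on a reading taken in its own setting. For the control arm, section 8.1 says "blood pressure readings measured for clinical purposes at the dialysis unit will be tracked, recorded and in response we will modify the dry weight". For the home arm, section 7.3 says "Home BP will be taken on a non-dialysis day", and only that arm is trained in home measurement at Visit 1. ABPM is therefore the one out-of-unit measure scheduled in both arms, which makes it useful for the secondary objective on blood pressure differences.

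Two features can weaken it:

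- **Uptake.** A participant who decides after learning the allocation may decide differently by arm. A home-arm participant has just been asked to take on home measurement; a control-arm participant has not. The two groups of recorders may then differ for reasons other than treatment.
- **End value.** If treatment is changed at Visit 9 and the cuff is placed afterwards, the 44 hours may partly reflect a change made after the 4-month regimen. The share of participants changed can differ by arm, because the two arms are judged on different readings.

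**Working it through.** The sample size of 50 was set by budget, with no SD, effect size or dropout rate, so there is no planned precision to reproduce. The one related figure that can be checked is the discordance in section 2: 166/269 = 61.7%, which agrees with the stated 62%. All uptake, gap, SD and effect values below are assumptions.

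**1. Order of steps**

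| Visit | Listed items | Order fixed in the text? |
|---|---|---|
| 1 | Randomisation (3), home training (4), ABPM (6) | Only by list position |
| 9 | Visit 2-8 procedures including adjustment (1), ABPM (4) | No |

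Appendix 1 marks no adjustment at Visit 1. The baseline recording is therefore not shown to be affected by protocol titration; the Visit 1 issue is selective uptake.

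**2. Selective uptake**

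Let u be uptake in one arm and g the gap between recorders and non-recorders in the quantity summarised. The recorders' mean differs from the whole-arm mean by (1 - u) × g. If change from baseline is analysed, g must be a gap in change, because a constant gap in level cancels.

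- u = 90%, g = 5 mmHg: 0.1 × 5 = 0.5 mmHg
- u = 50%, g = 10 mmHg: 0.5 × 10 = 5.0 mmHg
- u = 30%, g = 15 mmHg: 0.7 × 15 = 10.5 mmHg

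These are shifts in one arm. The between-arm comparison is biased only by the part that the other arm does not share.

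**3. Adjustment at Visit 9**

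Bias = (between-arm difference in the share adjusted before the recording) × (effect within 44 hours, assumed 2-10 mmHg).

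- Difference of 10 percentage points: 0.10 × 2 = 0.2 to 0.10 × 10 = 1.0 mmHg
- Difference of 62 points, a deliberately generous ceiling: 0.62 × 2 = 1.2 to 0.62 × 10 = 6.2 mmHg

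The 62% applies only to cohort members with unit SBP above 140 mmHg. Over the whole cohort, 166/377 = 44%, which gives 0.44 × 2 = 0.9 to 0.44 × 10 = 4.4 mmHg.

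**4. Sampling error for comparison**

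The 95% half-width for a difference in means is t × SD × √(2/n), with SD 20 mmHg assumed.

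- n = 25 per arm: 2.011 × 20 × √(2/25) = 11.4 mmHg (8.5-14.2 for SD 15-25)
- n = 13 per arm (about 50% uptake): 2.064 × 20 × √(2/13) = 16.2 mmHg (12.1-20.2)
- n = 8 per arm (about 30% uptake): 2.1448 × 20 × √(2/8) = 21.4 mmHg (16.1-26.8)

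**5. Would excluding adjusted participants help?**

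No. Adjustment is triggered by the reading that guides each arm, so exclusion selects on blood pressure after randomisation, and by a different reading in each arm. Suppose the highest 30% on the guiding reading are dropped in each arm (assumed), with SD 20. The mean of the retained guiding readings falls by 0.497 × 20 = 9.9 mmHg. ABPM falls by that amount times its correlation with the guiding reading:

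- Home arm, correlation 0.70 (assumed): 9.9 × 0.70 = 7.0 mmHg
- Control arm, correlation 0.34 (the figure in section 2 for unit against out-of-unit SBP, read as a correlation coefficient): 9.9 × 0.34 = 3.4 mmHg

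The spurious difference is 0.497 × 20 × (0.70 - 0.34) = 3.6 mmHg in favour of the home arm (1.6-4.6 for a home correlation of 0.5-0.8).

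**The case against.** The strongest reply is that post-randomisation choice is inferred from list order. The Visit 1 list is not strictly chronological: item 7, a blood sample taken at the start of dialysis, comes last. Item 6 says when the cuff is placed, not when agreement is given. Consent is obtained at Visit 0, and the consent form is not among the documents reviewed, so an ABPM choice may already be recorded there. This stands. A reader might infer that participants are shown to choose ABPM knowing their arm, but the documents neither require nor exclude earlier agreement. The gap is that no protocol step requires it, and the final recording is again labelled optional after four months in a known arm.

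A reader might also infer that ABPM is the only arm-neutral blood pressure outcome. Post-dialysis pressure is also compared in both arms and is neither arm's named target, while ABPM lies nearer the home arm's setting. Only the narrower description, the one out-of-unit measure scheduled in both arms, is supported.

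Third, section 5.2 describes monitoring from beginning to end and section 14.4 refers to changes, so a stable difference in level between willing and unwilling participants largely cancels in paired recordings. That also stands. Bias then requires willingness to be related to the change itself, or the summary to use final values alone.

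Fourth, the algorithm in section 8.1 starts with dry weight. On a thrice-weekly schedule 44 hours is roughly one interval between sessions, so a dry-weight change applied from the next session has little time to act. A change made in the same session, or to medication, could still matter.

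**Conclusion.** The point holds as a minor gap in design and reporting. ABPM uptake can depend on arm, because the trial is open-label and no protocol step requires agreement before randomisation. The end recording can follow a Visit 9 treatment change, because the two are not ordered.

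The possible distortion is a 0.5-10.5 mmHg shift in one arm from selection and 0.2-6.2 mmHg between arms from a Visit 9 adjustment, entirely under assumed inputs and with the upper ends generous. It is mostly smaller than the sampling error. Sampling error, however, will show in the reported SD and n; selection and late changes will not unless they are recorded.

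A reader might go further and say that the randomised comparison is broken. The documents do not support that: they show a possibility, not that uptake differs by arm. The outcome is optional, secondary and descriptive, in a pilot not designed to find differences between arms.

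**What to change.** - **Agreement.** In section 9.1, or before item 3 of section 9.2, obtain and record agreement to both ABPM recordings before randomisation. If the consent form already does this, say so in the protocol.
- **Analysis set.** In the SAP that section 14 says is still to be written, define the ABPM set as those who agreed before randomisation, analysed by randomised arm. Report uptake, completion and the baseline characteristics of recorders by arm.
- **Final recording.** State its timing relative to any Visit 9 adjustment, for example by scheduling it so that it is complete before Visit 9. Record on the CRF whether any change took effect before or during the 44 hours.
- **Summary.** Keep all final recordings in the main summary and use the flag only for a sensitivity description. Do not exclude adjusted participants.

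The cost is one agreement field, one CRF field and slightly tighter scheduling around the last visit. Earlier agreement does not prevent arm-dependent non-completion at 4 months, so completion by arm must be shown.

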## **9.3 Visits 2-8 (occurring approximately every 2 weeks)**

1. Record any Adverse Experiences
2. Review any home BP measures (if applicable)
3. Concomitant medications review
4. Updated medical history/interim events/interim hospitalizations
5. BP medication review and assessment of adherence to BP medications

6. Review dialysis unit records: estimated dry weight, pre-dialysis blood pressures, episodes of intra-dialytic hypotension
7. Record any updated laboratory values (with corresponding date) taken from the dialysis records
8. Record vital signs, including weight and dialysis unit BP
9. Administer questionnaire of symptoms of hypotension during the last hemodialysis session: cramping (yes/no), dizziness/lightheadedness (yes/no), and fatigue (yes/no).
10. Ask open-ended question: "How long did it take you to recover from your last dialysis session" (responses in minutes or hours)
11. If subject is a woman of child-bearing age, she will also be asked about possible pregnancy (UW only).
12. Adjust estimated dry weight and medications as per study physician's recommendations

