### 6.3 Exclusion Criteria

1. Pregnancy, anticipated pregnancy, or breastfeeding as this will require increase to more than three times a week dialysis and/or preclude use of some classes of blood pressure medications
2. Incarceration or institutionalized living which may prohibit measurement of home blood pressure
3. Participation in another intervention study that may affect blood pressure
4. Patients in whom systolic blood pressure is not measurable (e.g. those with left ventricular assist devices)
5. Hypotension: average pre-dialysis systolic blood pressure <100 mmHg over last 2 weeks prior to screening while not taking any blood pressure medications
6. Life expectancy <4 months
7. Anticipated living donor kidney transplant within 4 months

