## **10 ADVERSE EXPERIENCE REPORTING AND DOCUMENTATION**

### **10.1 Adverse Events**

An adverse event (AE) is any untoward medical occurrence during a clinical investigation and that does not necessarily have a causal relationship with the study intervention. An AE is therefore any unfavorable and unintended sign (including an abnormal laboratory finding), symptom or disease that may or may not be associated with the administration of a study intervention.

The study team will probe, via discussion with the subject and review of the medical record, for the occurrence of AEs during each subject visit and record the information in the site's source documents. Adverse events will be recorded in the patient CRF. Adverse events will be described by duration (start and stop dates and times), severity, outcome, treatment and relation to study intervention, or if unrelated, the cause.

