## **11 DISCONTINUATION AND REPLACEMENT OF SUBJECTS**

### **11.1 Early Discontinuation of Study Intervention**

A subject may be discontinued from study intervention at any time if the subject or the investigator (Sponsor) feels that it is not in the subject's best interest to continue. The following is a list of possible reasons for study treatment discontinuation:

- Subject withdrawal of consent
- Subject is not adherent with study procedures
- Adverse event that in the opinion of the investigator would be in the best interest of the subject to discontinue study treatment
- Protocol violation requiring discontinuation of study treatment

- Lost to follow-up

If a subject is withdrawn from treatment due to an adverse event, the subject will be followed and treated by the investigator until the abnormal parameter or symptom has resolved or stabilized.

All subjects are free to withdraw from participation at any time, for any reason, specified or unspecified, and without prejudice.

Reasonable attempts will be made by the investigator to provide a reason for subject withdrawals. The reason for the subject's withdrawal from the study will be specified in the subject's source documents. Subjects enrolled at least 1 month should be encouraged to come in for a final visit (and the procedures to be followed would include those for their next scheduled visit).

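### The pregnancy question during treatment is asked at UW only, although the pregnancy exclusion and the two-weekly drug algorithm apply at both sites

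*Combined protocol and SAP*

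**What the plan says.** Section 6.3 item 1 excludes pregnancy, anticipated pregnancy and breastfeeding at both sites. The reason given is that "this will require increase to more than three times a week dialysis and/or preclude use of some classes of blood pressure medications".

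After randomization, the only pregnancy check in the protocol is section 9.3 item 11, for Visits 2-8: "If subject is a woman of child-bearing age, she will also be asked about possible pregnancy (UW only". Section 9.4 item 1 sets the final visit by reference, "Same procedures listed in for visits 2-8", so the restriction carries over to Visit 9. Appendix 1 has no row for a pregnancy question at either site.

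Treatment is not restricted by site. Section 8.1 describes one algorithm to be used "in both treatment groups, which will be implemented every 2 weeks". For SBP above 140 mmHg it first lowers dry weight, then raises doses of existing drugs. If those are at their tolerated maximum, the team "will add doses (and titrate up) of new medication" classes. RAAS inhibitors come first in both the dose-raising and the add-on order. Section 9.3 item 12, listed straight after the pregnancy question, is the point of action: "Adjust estimated dry weight and medications as per study" physician's advice. Section 7.1 stratifies randomization by site, so both arms run at UCSF and at UW.

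**The concern.** The protocol treats pregnancy as incompatible with the intervention because of the dialysis schedule and the drugs. Neither reason ends at enrolment. A woman who becomes pregnant in month two is exposed to the same titration that made pregnancy a reason to exclude her at entry.

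At UW she is asked about pregnancy at each contact where drugs may be changed. At UCSF the same changes can be made without anyone being required to ask. A UCSF pregnancy would come to light only if she volunteered it or if general history, record or adverse-event review picked it up, and antihypertensives could be increased or added in the meantime.

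This is a subject-safety point. It does not bear on the sample size, the estimates or any comparison between arms.

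**Working it through.** The plan states no figure on this point, so the check compares sections and counts contacts.

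**Sections compared**

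| Element | UW | UCSF | Source |
|---|---|---|---|
| Pregnancy exclusion at entry | yes | yes | 6.3 item 1, no site limit |
| Serum pregnancy test at screening | yes | unclear | 8.3 names UW; 9.1 item 10 gives no site limit |
| Two-weekly dry-weight and drug algorithm | yes | yes | 8.1, 9.3 item 12 |
| Dose increases and new drug classes | yes | yes | 8.1, step for SBP above 140 mmHg |
| Pregnancy question, Visits 2-8 | yes | no | 9.3 item 11 |
| Pregnancy question, Visit 9 | yes | no | 9.4 item 1, by reference |
| General history, laboratory and AE review | yes | yes | 9.3 items 1, 4, 6 and 7; 10.1 |

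That both sites use the same algorithm is inferred from the absence of any site qualifier in 8.1 and from the site-stratified randomization. Nothing in the documents contradicts it.

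**Is there a visible reason for the site limit?** The other procedures assigned to UW (8.3; 9.2 item 7; 9.4 item 2) are blood collections, for which sampling arrangements could explain a restriction. Item 11 is an interview question that needs no sample.

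**Exposure per woman of child-bearing age**

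- Follow-up contacts: Visits 2 to 9 = 8.
- Contacts with the question: 8 of 8 at UW, 0 of 8 at UCSF.
- Spacing in Appendix 1 is 14 ± 7 days, so a UW woman is asked about every 7 to 21 days.
- Time without the question at UCSF: 8 × 14 = 112 days, about the whole 4-month period.

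**Exposure at the site**

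- UCSF plans 25 of the 50 participants (section 6.4). The number of women of child-bearing age is not given.
- Assumption, not from the documents: 1 to 5 such women, which is 1/25 = 4% to 5/25 = 20%.
- Contacts without the question: 1 × 8 = 8 to 5 × 8 = 40.

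These counts describe what the protocol requires. They are not a forecast of pregnancies or of harm.

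**The case against.** The strongest reply is that nothing here is contradictory. Section 6.3 is an entry criterion, and no section promises pregnancy surveillance during treatment at either site. UW has an additional safeguard, and since 8.3 also names UW for the screening test, item 11 may be the follow-up half of a deliberate local arrangement, perhaps an IRB requirement. Women anticipating pregnancy are excluded at both sites. Every contact at both sites includes updated history, laboratory values and medication review, and section 10.1 has staff probe "for the occurrence of AEs during each subject visit". Drug changes pass through a study physician, doses stay within approved ranges (2.1), and section 11.1 already says "A subject may be discontinued from study intervention at any time" when that is in her interest. UCSF staff are not barred from asking. The consent form, which is not among the documents available here, may tell women to report a pregnancy. Finally, deleting the restriction adds a question but no rule for a positive answer.

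Much of this stands. It is a monitoring gap, not a contradiction. The event is rare, the order of a numbered list does not prove a required sequence, and Visit 9 is where the question protects least.

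What it does not supply is a direct pregnancy check at UCSF or a stated reason for going without one. The general routes do not name pregnancy, and a newly recognised pregnancy does not clearly fit the adverse-event definition in 10.1. Visits 2-8 may also be telephone calls (Appendix 1), which makes incidental detection less likely. The physician's decision and the stopping clause help only once the pregnancy is known. A local requirement would explain why UW asks, but not why women at UCSF on the same treatment should not be asked.

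**Conclusion.** The point holds. Item 11 gives UCSF women weaker protection than UW women under the same algorithm, without explanation. The difference is 8 of 8 against 0 of 8 contacts per woman, over about 112 days. On the assumption of 1 to 5 such women at UCSF, that is 8 to 40 contacts without the question. The number of pregnancies is expected to be small and may be zero.

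The conclusion rests on two readings: that the algorithm applies equally at both sites, and that no pregnancy check outside the available text covers UCSF. The wording of item 11 is certain; the practical harm is uncertain. The change should be made because the possible harm is serious and the remedy costs almost nothing. No effect on the analysis is claimed.

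**What to change.** Delete the parenthetical UW-only restriction from section 9.3 item 11. Both sites then ask women of child-bearing age at Visits 2-8 and, through section 9.4 item 1, at Visit 9, before any adjustment under item 12. A positive answer goes to the study physician, who decides on adjustment under item 12 and can stop the intervention under 11.1.

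Optionally, name pregnancy among the possible reasons for discontinuation in 11.1. This is not essential, because the general best-interest clause already permits stopping. The same amendment could also settle whether the screening pregnancy test is done at UCSF, where 8.3 and 9.1 item 10 leave doubt.

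The cost is two words in an IRB-approved amendment and one more interview question per contact at UCSF. The main change needs no new test, visit or staff.
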